### **11.3 RECORDING AEs AND SAEs**

When an AE/SAE occurs, it is the responsibility of the Investigator, or another suitably qualified physician in the research team who is delegated to record and report AEs/SAEs, to review all documentation (e.g. hospital notes, laboratory and diagnostic reports) related to the event. The Investigator will then record all relevant information in the eCRF/AE log and on the SAE form (if the AE meets the criteria of serious).

Information to be collected includes dose, type of event, onset date, Investigator assessment of severity and causality, date of resolution as well as treatment required, investigations needed and outcome.

#### **11.3.1 Pre-existing Medical Conditions**

Pre-existing medical conditions (i.e. existed prior to informed consent) should be recorded as medical history and only recorded as adverse events if medically judged to have worsened during the study.

#### **11.3.2 Worsening of the Underlying Condition during the Trial**

Medical occurrences or symptoms of deterioration that are expected due to the participant's underlying condition should be recorded in the patient's medical notes and only be recorded as AEs on the AE log if medically judged to have unexpectedly worsened during the study. Events that are consistent with the expected progression of the underlying disease should not be recorded as AEs.

### **11.4 ASSESSMENT OF AEs AND SAEs**

Each AE must be assessed for seriousness, causality, severity and ARs must be assessed for expectedness by the Principal Investigator or another suitably qualified physician in the research team who has been delegated this role. For randomised double blind studies, AEs will be assessed as though the participant is taking active IMP. SUSARs will be unblinded by ACCORD before they are reported to REC and CA (by ACCORD). The Chief Investigator (CI) may not downgrade an event that has been assessed by an Investigator as an SAE or SUSAR, but can upgrade an AE to an SAE, SAR or SUSAR if appropriate.

#### **11.4.1 Assessment of Seriousness**

The Investigator will make an assessment of seriousness as defined in Section 11.1.

#### **11.4.2 Assessment of Causality**

The Investigator will make an assessment of whether the AE/SAE is likely to be related to the IMP according to the definitions below.

**Unrelated:** where an event is not considered to be related to the IMP.

**Possibly Related:** The nature of the event, the underlying medical condition, concomitant medication or temporal relationship make it possible that the AE has a causal relationship to the study drug. Where non Investigational Medicinal Products (NIMPs) e.g. rescue/escape drugs are given: if the AE is considered to be related to an interaction between the IMP and the NIMP, or where the AE might be linked to either the IMP or the NIMP but cannot be clearly attributed to either one of these, the event will be considered as an AR. Alternative causes such as natural history of the underlying disease, other risk factors and the temporal relationship of the event to the treatment should be considered and investigated. The blind should not be broken for the purpose of making this assessment.

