
Secondary Endpoints
	
 
1. In-hospital mortality and 90-day mortality;
 
2. Time to start of IMP;
 
3. Data completeness;
 
4. Study withdrawal;
 
5. Volume of randomised fluid delivered in each arm in the first 6hrs and 24hrs;
 
6. Proportion of participants needing critical care intervention: Intravenous vasopressors, renal replacement therapy and invasive ventilation;
 
7. Proportion of patients who receive any other fluid apart from intervention or control in first 6 hrs after recruitment;
 
8. Proportion of patients admitted to critical care (HDU/ICU); length of stay in critical care (HDU/ICU);
 
9. Length of hospital stay;
 
10. Proportion of patients readmitted in first 90 days after discharge.
 
11. Proportion of patients developing any of: acute kidney injury (Defined by NICE (https://cks.nice.org.uk/acute-kidney-injury#!scenario)); pulmonary oedema (Radiology diagnosis or requirement for rescue management (new diuretic use); and allergy or anaphylaxis (Requirement for rescue management (antihistamines, adrenaline, intravenous fluids, steroids)).
 
12. Health Related Quality of life (EQ-5D-5L) at 7 and 180 days for the first 50 patients.
 
13. Secondary care costs at 30 days (calculated from readmissions and length of stay at ward level and in critical care (HDU/ICU).
 

IMP(s)
	
5% Human Albumin Solution

IMP Route of Administration
	
Intravenous, peripheral or central

Lay Summary of Trial
	
The aim of this research study is to compare two different fluids (Human Albumin Solution (HAS) and Balanced Crystalloid that are given via a drip to patients with severe infection (sepsis). We plan to see which fluid is better, and to see if they have a role in improving a patient’s recovery time, reducing complications and the length of time they stay in hospital. This study plans to find out if there is evidence that one fluid is better overall to determine the need for a subsequent definitive trial.

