## **6.7 OTHER MEDICATIONS**

### **6.7.1 Non-Investigational Medicinal Products**

There are no NIMPs for this study.

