### 11.1 DEFINITIONS

An **adverse event** (AE) is any untoward medical occurrence in a clinical trial participant which does not necessarily have a causal relationship with an investigational medicinal product (IMP).

An **adverse reaction** (AR) is any untoward and unintended response to an IMP which is related to any dose administered to that participant.

A **serious adverse event** (SAE), **serious adverse reaction** (SAR). Any AE or AR that at any dose:

- results in death of the clinical trial participant;
- is life threatening\*;
- requires in-patient hospitalisation^ or prolongation of existing hospitalisation;
- results in persistent or significant disability or incapacity;
- consists of a congenital anomaly or birth defect;
- results in any other significant medical event not meeting the criteria above.

\*Life-threatening in the definition of an SAE or SAR refers to an event where the participant was at risk of death at the time of the event. It does not refer to an event which hypothetically might have caused death if it were more severe.

^Any hospitalisation that was planned prior to enrolment will not meet SAE criteria. Any hospitalisation that is planned post enrolment will meet the SAE criteria.

A **suspected unexpected serious adverse reaction** (SUSAR) is any AR that is classified as serious and is suspected to be related to the IMP, that it is not consistent with the information about the IMP in the Summary of Product Characteristics (SPC) booklet or Investigators Brochure.

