## 4.7 Safety

Summary tables of adverse events, by treatment group and overall. Number of events and number of patients who had an event, showing all adverse events, serious adverse events, and non-serious adverse events. Tables will also be presented, stratifying events by MedDRA code; severity; relatedness; expectedness; and outcome.

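### The protocol does not settle whether balanced crystalloid counts as an investigational product for safety assessment, so relatedness, expectedness and SAR/SUSAR status may not be comparable between arms

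*Protocol*

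**What the plan says.** **Text that ties safety assessment to albumin**
- The IMP(s) row of the Trial Summary has one entry, "5% Human Albumin Solution". The title of section 6 names the IMP and the comparator separately.
- Section 11.1 defines an adverse reaction as "any untoward and unintended response to an IMP which is related to any dose administered to that participant", and a SUSAR as "any AR that is classified as serious and is suspected to be related to the IMP".
- Section 11.4.2 sets the causality question: "The Investigator will make an assessment of whether the AE/SAE is likely to be related to the IMP according to the definitions below". An event is Unrelated when it is not thought to be related to the IMP.
- Section 11.4.3 judges expectedness against the IMP's toxicity as listed in the SPC booklet.
- Section 6.7.1 adds: "There are no NIMPs for this study".

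**Text that treats crystalloid as a study product**
- Section 6.2 describes balanced crystalloid under headings that call it a study drug. Section 6.2.7 provides a representative SPC for it, checked and signed by the chief investigator and the sponsor, as for albumin.
- In section 11.4.2 the Possibly Related category applies where the circumstances "make it possible that the AE has a causal relationship to the study drug". The term changes from IMP to study drug.
- SAP 4.3 summarises the time from randomisation to the start of the IMP for each treatment group.

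**Analysis**
- SAP 4.7 plans adverse event summaries by treatment group, then further tables "stratifying events by MedDRA code; severity; relatedness; expectedness; and outcome". It does not say to which product an event is related.

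**The concern.** The trial compares two allocated fluids, and a safety comparison needs the same causality question in both arms. If the question is only whether albumin caused the event, a reaction to crystalloid in a participant who received no albumin can only be answered no. It would then not be an adverse reaction, and could not be a SAR or a SUSAR. Under section 11.7 the annual DSUR lists SARs and SUSARs, so the event would be missing there as well as from expedited reporting. In the SAP 4.7 tables, related events could arise from one fluid and not from the other, and the difference would run against albumin. Sites that read the study-drug wording more broadly would code the same event differently, so coding could also vary between sites.

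**Working it through.** No arithmetic applies, because the point depends on definitions and not on a rate or a sample size. The check follows one case through the text: a serious reaction to crystalloid, not on the exemption list, in a control participant who received no albumin.

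1. **Is crystalloid an IMP?** By the Trial Summary row, no. By the per-arm use of time to start of IMP in SAP 4.3, yes, since that measure has no meaning in the control arm otherwise. Section 6.2 calls it both a comparator and a study drug. No sentence settles the matter for section 11.
2. **Causality (11.4.2).** By the opening question and the Unrelated category, the answer is Unrelated. By the Possibly Related category, which speaks of the study drug, it could be Possibly Related.
3. **Adverse reaction, SAR, SUSAR (11.1).** Each needs a relation to an IMP. On the literal reading of step 1 the event meets none of them.
4. **Expectedness (11.4.3).** The reference is the toxicity of the IMP. A crystalloid SPC is on file, but this section does not say that it is to be used.
5. **Reporting.** Section 11.6.2 has non-exempt SAEs reported to the sponsor in both arms whatever their relatedness, so the event is still counted as an SAE. Only its SAR/SUSAR classification, and with it the DSUR listing, is lost.
6. **Analysis (SAP 4.7).** The event is counted as an SAE. On the literal reading it goes in the unrelated row and has no expectedness assessment.

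**How many events are in play**
- Allocation is 1:1 with 300 planned, so about 300 × 1/2 = 150 participants are allocated the fluid whose status is unclear. That is the number exposed to the ambiguity, not a number of misclassified events.
- Section 11.6.2 exempts allergy or anaphylaxis, pulmonary oedema, acute kidney injury, critical care admission and infection-related death from sponsor reporting. Under section 11.5 only serious, reportable events reach the AE log or SAE form. The reactions most readily attributed to a fluid are therefore largely absent from the relatedness table in both arms.
- Acute kidney injury, pulmonary oedema and allergy or anaphylaxis are summarised by randomised group as outcomes (SAP 4.6), with no causality judgement.

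**Mixed exposure.** Section 6.3 allows crystalloid as maintenance fluid in the albumin arm, section 6.5 provides for crossover, and SAP section 3 analyses safety by treatment received first. The definitions do not say how to attribute a reaction when both fluids were given.

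**The case against.** The strongest reply is that the protocol contains no bar. Its own Possibly Related category uses the term study drug, section 6.2 applies that term to crystalloid, and a verified crystalloid SPC is on file. A sensible site could assess a crystalloid reaction in full. That stands, and it makes this an inconsistency and not a prohibition. A reader might infer that a crystalloid reaction can never be classed as a SAR or SUSAR; the documents support that only on the literal reading.

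Three other inferences also go too far.
- **The statement that there are no NIMPs causes the gap.** It adds little. The NIMP clause in 11.4.2 makes an event an adverse reaction only through an interaction with the IMP, or where the two cannot be told apart. Calling crystalloid a NIMP would not make a reaction to crystalloid alone an adverse reaction.
- **The control arm's related count must be zero.** Even on the literal reading this fails. A participant allocated crystalloid who crosses over can have an albumin-related event, and the descriptive ITT safety summary counts it in the control arm.
- **SAP 4.7 commits to relatedness by arm.** The phrase about treatment group belongs to the first summary tables; the sentence on relatedness does not repeat it. A by-arm display is likely but inferred.

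It is also fair to say that the main safety comparison survives, that anaphylaxis data go to the DMC, that the protocol calls its analyses exploratory and mainly descriptive, and that no decision hangs on the relatedness table. This limits the consequence but does not resolve the contradiction.

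**Conclusion.** The point holds as an internal inconsistency with a one-sided result on its literal reading. It affects the relatedness, expectedness and SAR/SUSAR status of serious events outside the exemption list. SAE counts and the three complication outcomes stay comparable between arms. The residual set of events is probably small. The documents give no rate for it, so no count of misclassified events can be supported, and a figure built on an assumed rate would mislead. The conclusion assumes that at least some sites follow the IMP wording as written, and that SAP 4.7 will be read by arm. It is worth correcting because the cost is low and because, uncorrected, a related-events row could be read as evidence against albumin.

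**What to change.** **Protocol.** In 11.1 and 11.4.2–11.4.3, word causality as relation to the study fluid or fluids received (5% HAS or balanced crystalloid), and judge expectedness against that fluid's own representative SPC. Use one term throughout, and reconcile the IMP(s) row and section 6 with it. The formal regulatory classification of crystalloid is for the sponsor.

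**SAP 4.7.** State that relatedness is to the study fluid received. The SAP abstract describes recruitment in the past tense, so coding may already be done. If it was done against albumin only, state this and add that relatedness and expectedness must not be compared between arms.

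**Cost.** Wording only, since the crystalloid SPC is already in the TMF. The small downside is a few more causality and expectedness assessments in the control arm.

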#### 11.4.3 Assessment of Expectedness

If the event is an AR the evaluation of expectedness will be made based on knowledge of the reaction and the relevant product information documented in the SPC Booklet

The event may be classed as either:

**Expected:** the AR is consistent with the toxicity of the IMP listed in the SPC Booklet.

**Unexpected:** the AR is not consistent with the toxicity in the SPC Booklet.

Fatal and life threatening SARs should usually be considered unexpected. Fatal SARs can only be expected for IMPs with an MA in the EU, when it is clearly stated in the list of ARs of the SPC (Section 4.8) that the IMP causes fatal SARs.

#### 11.4.4 Assessment of Severity

The Investigator will make an assessment of severity for each AE/SAE/SAR/SUSAR and record this on the eCRF/AE log or SAE form according to one of the following categories:

**Mild:** an event that is easily tolerated by the participant, causing minimal discomfort and not interfering with every day activities.

**Moderate:** an event that is sufficiently discomforting to interfere with normal everyday activities.

**Severe:** an event that prevents normal everyday activities.

Note: the term 'severe', used to describe the intensity, should not be confused with 'serious' which is a regulatory definition based on participant/event outcome or action criteria. For example, a headache may be severe but not serious, while a minor stroke is serious but may not be severe.

### 11.5 RECORDING OF AEs

All adverse events identified between consent and 7 days after randomisation for each participant will be recorded in the medical notes for each participant. Only those events which would meet the criteria of seriousness and also qualify for reporting to the sponsor (see section 11.6.2) will be recorded on AE logs/ SAE forms and will be assigned the appropriate MedDRA Systems Organ Class (SOC) code.

### 11.6 REPORTING OF SAEs/SARs/SUSARs

Once the Investigator becomes aware that an SAE has occurred in a study participant, the information will be reported to the ACCORD Research Governance **within 24 hours**. If the Investigator does not have all information regarding an SAE, they

should not wait for this additional information before notifying ACCORD. The SAE report form can be updated when the additional information is received.

The SAE report will provide an assessment of causality and expectedness at the time of the initial report to ACCORD according to Sections 10.4.2, Assessment of Causality and 10.4.3, Assessment of Expectedness.

The SAE form will be transmitted via email to [[contact]](mailto:[contact]). Only forms in a pdf format will be accepted by ACCORD via email. Where missing information has not been sent to ACCORD after an initial report, ACCORD will contact the Investigator and request the missing information. The Investigator must respond to these requests in a timely manner.

All reports sent to ACCORD and any follow up information will be retained by the Investigator in the Investigator Site File (ISF).

### **11.6.2 Reporting of SAEs/SARs/SUSARs and exemptions**

All SAEs that meet the definition given in section 11.1 and occur between consent and 7 days afterwards should be reported to the Sponsor unless they meet the exemption criteria below. These are outcome events are anticipated to occur in this participant group and will be exempt from reporting to the Sponsor:

Death related to infection (including multi-organ failure)

Critical care (HDU/ICU) admission

Acute kidney injury

Pulmonary oedema,

Allergy or anaphylaxis

Events That Are Common in the Trial Population:

The primary event of infection is classified as a pre-existing condition. As such, the occurrence or expected progression of infection or sepsis-related events including death will occur. In addition, participants are likely to have many minor adverse events during the course of the trial. These events will be recorded in the medical records and assessed in the same way as AE/SAEs. However, they are not usually recorded as AEs/SAEs, unless they are thought to be related to participant involvement in the trial.

Abdominal pain, nonspecific or related to a pre-existing condition

Accidents (domestic, traffic, occupational) including falls

Agitation or Anxiety

Atrial fibrillation or another cardiac dysrhythmia

Bleeding

Blood result abnormality (outside lab reported normal range) requiring no clinical intervention

Breathlessness related to a pre-existing condition e.g. COPD

Chest pain, non-specific or related to a pre-existing condition

Confusion or delirium

Constipation

Deep vein thrombosis/venous thromboembolism

Diarrhoea and/or vomiting

Dizziness or light headedness including vertigo

Dysphagia

Embolism

Fatigue, tiredness or sleepiness (somnolence)

Gastrointestinal disturbance, non-specific

Headache

Hypotension (if related to infection)

Hypoxia (if related to infection)

Incontinence, urinary or faecal

Malignancy, new diagnosis or new treatment for existing diagnosis

Mild ankle swelling not requiring treatment

Mood disorders

Muscle twitching

Any musculoskeletal condition e.g. arthritis or mechanical back pain

Peripheral vascular disease

Pneumothorax

Pressure sores or skin ulceration

Procedures occurring as part of the management of infection e.g. urinary catheter, central venous line, arterial line, intubation

Seizure

Sinus tachycardia (if related to infection)

Visual Loss e.g. cataract or macular degeneration or retinal detachment

Weight loss

Any other known complications of, or symptoms related to infection or sepsis

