# As Day 30 and Day 90 follow up is collected from the medical records it can be reviewed and recorded in the eCRF up to 7 days after the time point so it captures all admissions/events up to and including Day 30 and 90.

For the first 50 participants enrolled in the study, HRQoL will be measured using the EQ-5D-5L at baseline, 7 days and at 180 days. If questionnaires are not completed on the specified day or are not returned by the participant, this will not be reported as a deviation. Vital status will be checked either using local electronic medical records or contact with participant GP prior to contacting participant. Outcome measures will be obtained via the medical notes.

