### 11.2 IDENTIFYING AEs AND SAEs

Participants will be asked about the occurrence of AEs/SAEs during the study and the medical records will be reviewed to identify these. AEs and SAEs will only be recorded and reported from consent until 7 days after randomisation due to the well-known safety profiles of the interventions. Open-ended and non-leading verbal questioning of

the participant will be used to enquire about AE/SAE occurrence. Participants will also be asked if they have been admitted to hospital, had any accidents, used any new medicines or changed concomitant medication regimens. If there is any doubt as to whether a clinical observation is an AE, the event will be recorded.

AEs and SAEs may also be identified via information from support departments e.g. laboratories.

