## **11.7 REGULATORY REPORTING REQUIREMENTS**

ACCORD is responsible for pharmacovigilance reporting on behalf of the co-sponsors (The University of Edinburgh and NHS Lothian).

ACCORD has a legal responsibility to notify the regulatory competent authority and relevant ethics committee (Research Ethics Committee (REC) that approved the trial). Fatal or life threatening SUSARs will be reported no later than 7 calendar days and all other SUSARs will be reported no later than 15 calendar days after ACCORD is first aware of the reaction.

ACCORD (or delegate) will inform Investigators at participating sites of all SUSARs and any other arising safety information.

ACCORD will be responsible for providing safety line listings and assistance; however, it is the responsibility of the Investigator to prepare the Development Safety Update

Report. This annual report lists all SARs and SUSARs reported during that time period. The responsibility of submitting the Development Safety Update Report to the regulatory authority and RECs, lies with ACCORD.

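### The 7-day safety limit has no exception for SARs or SUSARs: a suspected serious reaction starting after Day 7 is not reportable, and the sections conflict on late recognition

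*Protocol*

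**What the plan says.** - **Protocol 11.2:** "AEs and SAEs will only be recorded and reported from consent until 7 days after randomisation". The reason given is that the safety profiles of the interventions are well known.
- **Protocol 11.5:** "All adverse events identified between consent and 7 days after randomisation for each participant will be recorded in the medical notes". Only serious events that also qualify for sponsor reporting under 11.6.2 go on to AE logs and SAE forms.
- **Protocol 11.6:** the site reports an SAE to ACCORD within 24 hours of the investigator learning of it. That sentence carries no Day 7 limit.
- **Protocol 11.6.2:** "All SAEs that meet the definition given in section 11.1 and occur between consent and 7 days afterwards should be reported to the Sponsor", apart from the exempt outcomes listed after it. Its one relatedness clause, "unless they are thought to be related to participant involvement in the trial", belongs to the list of common events.
- **Protocol 11.1:** SAE and SAR share a single definition ("Any AE or AR that at any dose"). A SUSAR is a serious reaction not consistent with the product information.
- **Protocol 11.7:** "Fatal or life threatening SUSARs will be reported no later than 7 calendar days", and other SUSARs within 15, counted from when ACCORD is first aware.
- **Protocol 7.1:** the schedule collects adverse events at baseline, Days 1 to 6 and Day 7. Records are reviewed again around Day 30 and Day 90, "so it captures all admissions/events up to and including Day 30 and 90", but the rows marked there are mortality, stay (Day 90 only) and readmissions (Day 90 only).
- **SAP 4.7 and 4.9:** adverse events are tabulated, and adverse events and SUSARs are listed. No time limit is stated.

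**The concern.** A short window for unrelated events is ordinary in a population this ill. The stated reason does not stretch to suspected reactions, because a SUSAR is by definition an event that the known profile does not explain. A well-known profile is therefore no ground for closing the route to unexpected reactions at Day 7.

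The sponsor's duty to the regulator and ethics committee, the annual safety report and the SAP outputs all depend on what sites report. If sites follow 11.2 and 11.6.2 literally, an absence of late suspected reactions could reflect the rule rather than observation. The trial is meant to inform a larger one, so its safety record will be carried forward.

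**Working it through.** The plan gives no statistical figure to reproduce on this point. The check compares the sections that set or use the window.

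**1. Does the limit cover reactions?** Yes. Section 11.6.2 applies to SAEs as defined in 11.1, and that definition takes in SARs. SUSARs are a subset of serious reactions.

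**2. Is there an exception for related events?** None on timing. The relatedness clause in 11.6.2 brings related events back from the common-events list; it does not extend the window.

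**3. What does each section turn on?**

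| Protocol section | Turns on | End of window |
|---|---|---|
| 11.2 | recording and reporting | 7 days after randomisation |
| 11.5 | identification | 7 days after randomisation |
| 11.6 | investigator awareness (report in 24 hours) | none stated |
| 11.6.2 | occurrence | 7 days after consent |
| 7.1, adverse events row | collection | Day 7 |

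**4. Two test cases**, each a non-exempt serious event judged possibly related.

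- *Onset Day 9, noticed Day 9.* It is outside 11.2, 11.5 and 11.6.2. Section 11.6 read alone would require a report, but if it overrode the other sections their limit would have no effect. As written, the event is not reportable.
- *Onset Day 5, found at the Day 30 review.* It is inside 11.6.2 (it occurred in time) and 11.6 (24 hours from awareness). It is outside 11.2 and 11.5 (not recorded, reported or identified in time). The text conflicts.

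**5. Do other sections close the gap for late onset?** No. Section 11.7 governs what the sponsor passes on once a report has reached it. Section 11.8 follows events already recorded or reported. Under 11.5, an event that does not qualify under 11.6.2 reaches no AE log or SAE form, so it would probably also be absent from the SAP 4.7 tables and 4.9 listings.

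**6. Which clock?** The two end dates differ by the interval between consent and randomisation. Under deferred consent (5.2.3), the patient is allocated and treated before consent is sought, so the 11.6.2 window closes later than that in 11.2 and 11.5.

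**7. Arithmetic.**

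- Share of the 90-day follow-up inside the window: 7/90 = 7.8%. The remainder is 90 − 7 = 83 days, or 92.2%.
- For the first 50 participants, followed to 180 days: 7/180 = 3.9%.
- Window relative to treatment: (7 × 24 hours)/6 hours = 28 times.

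**The case against.** The strongest defence is that the window is a reasoned choice. Both fluids are licensed products, treatment lasts 6 hours, and 7 days is 28 times that period. Neither document describes a late-onset reaction to either fluid. Some late harm is captured elsewhere: acute kidney injury, pulmonary oedema and allergy or anaphylaxis are collected at discharge, which may fall after Day 7. Mortality and readmissions are collected to Day 90, and the DMC sees anaphylaxis data.

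Much of this stands. It supports the 7-day limit for unrelated SAEs and makes late reactions probably few. Several of the likeliest harms are also exempt from sponsor reporting at any time under 11.6.2, so the gap concerns the remaining reactions. But outcome data are not SAE reports to the sponsor, and a known profile cannot justify shutting out unexpected events.

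Two stronger readings are tempting and not supported:

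- A reader might infer that any reaction recognised after Day 7 has no route to the sponsor. For one that began by Day 7, 11.6 and 11.6.2 do provide a route, and 11.2 and 11.5 contradict it.
- A reader might take 7/90, or the number of participants still in hospital at Day 7, as a measure of missed reactions. Neither is. The 90 days are follow-up for mortality and readmission, not a period of risk after a 6-hour infusion, and being an inpatient says nothing about how often reactions occur.

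**Conclusion.** The point holds in a limited form. Read literally, the protocol does not make a non-exempt suspected serious reaction with onset after Day 7 reportable by the site, and nothing downstream repairs this. For onset by Day 7 with later recognition, the sections contradict each other and must be reconciled. The end of the window is also stated in two ways.

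The reporting window spans 7.8% of the 90-day follow-up, but the number of late reactions cannot be derived from the documents and is probably small. The case for change rests on the role of SUSAR reporting and the low cost of the repair, not on an expected count. It should be changed; it does not threaten the primary analyses.

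**What to change.** 1. Keep the 7-day limit for SAEs judged unrelated, and state one start point for it in 11.2, 11.5 and 11.6.2. Randomisation is the simpler choice: two of the three sections already count the 7 days from it, and every participant has that date, including those under deferred consent.
2. Add to 11.2 and 11.6.2, and align 11.5: *Subject to the exemptions in 11.6.2, any SAE judged possibly related to the IMP that the Investigator becomes aware of during the participant's follow-up is recorded and reported to ACCORD within 24 hours of awareness, whatever its date of onset.* This also settles the late-recognition conflict for related events. It leaves the exemption list intact and keeps causality tied to the IMP, as in 11.4.2.
3. State that no active adverse-event screening is added after Day 7. The Day 30 and Day 90 reviews keep their present content.
4. In SAP 4.7, list related events with onset after Day 7 separately, so that the counts by arm keep a fixed 7-day window.

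The cost is a few extra SAE forms and causality assessments. Late events would be captured only when noticed, and causality is judged against the IMP (5% HAS in the trial summary) in an open-label trial. They should therefore be listed and not compared between arms.
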